## 10.2 Populations for Analyses

For purposes of analysis, the following populations are defined:

Population	Description
Enrolled	All participants who sign informed consent
Randomized	All participants who are randomized to any study treatment arm of any track in this study
Treated	All participants who are randomized and take at least 1 dose of study treatment
PK	All treated participants who have evaluable concentration time data
Immunogenicity	All treated participants who have available immunogenicity assessment data
Biomarker	All treated participants who have available biomarker data

Population	Description
Response-evaluable	All treated participants with measurable disease and 1 of the following: 1) at least 1 postbaseline tumor measurement, 2) clinical progression, or 3) death

### 10.3 Statistical Analyses

The statistical analysis plan will be developed and finalized before database lock. Below is a summary of planned statistical analyses of the primary and secondary endpoints.

#### 10.3.1 Efficacy Analyses

The primary efficacy analyses will be performed on treated population for the final analysis. Efficacy analyses based on the response-evaluable population may be performed for interim analyses, when the minimum follow-up period is less than sufficient to warrant adequate interpretation of the result. Details on censoring scheme on time-to-event endpoints such as DOR, PFS, and OS will be described in the SAP.

Endpoint	Statistical Analysis Methods
ORR BOR for a participant will be assessed per RECIST v1.1 by investigator.	Estimate of ORR and corresponding 2-sided exact 95% CI will be derived using the Clopper-Pearson method by study treatment under each track.
Median DOR DOR for a participant with a BOR of CR or PR is defined as the time between the date of first response and the date of the first objectively documented tumor progression per RECIST v1.1 or death, whichever occurs first.	Median DOR using the Kaplan-Meier method and corresponding 2-sided 95% CI will be derived using Brookmeyer and Crowley methodology (using log-log transformation) by study treatment under each track.
PFSR at 24 weeks PFS for a participant is defined as the time from the first dosing date to the date of first objectively documented disease progression or death due to any cause, whichever occurs first.	Estimate by the Kaplan-Meier method and corresponding 95% CI will be derived based on Greenwood formula by study treatment under each track.
OS rate at certain time points OS for a participant is defined as the time from the first dosing date to the date of death due to any cause.	Estimate by the Kaplan-Meier method and corresponding 95% CI will be derived based on Greenwood formula by study treatment under each track.

Treatments under each track for different populations will be analyzed independently. There is no intention to combine the same study treatment across tracks for efficacy analyses.

Efficacy from retreatment will be assessed and analyzed separately from the initial treatment.

Participants re-randomized into Track 2 will be combined with participants originally randomized into Track 2 for efficacy analysis.

Specific analyses to be performed for each track are shown in [Table 10.3.1-1](#).

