**Table 2-3: Follow-up Procedural Outline**

Procedure	Safety Follow-up a			Notes
	FU 1 30 Days (± 7 Days)	FU 2 60 Days (± 7 Days)	FU 3 100 Days (± 7 Days)	
Patient-reported Outcomes Assessment c	X	X	X	EQ-5D-3L and GaCS and/or ECS Can be collected by telephone at regularly scheduled times
Collection of Survival Status and Subsequent Treatment Information c	X	X	X	Safety follow-up visits must occur in the office. Response (and survival) follow-up visits may be performed by telephone contact or clinic visit.

a FU visits at 30, 60, and 100 days (± 7 days) should occur after the last dose of study treatment or coinciding with the date of discontinuation ± 7 days, if the date of discontinuation is greater than 30 days after the last dose, to monitor for AEs.

b Not applicable as of Protocol Amendment 06: Additional survival follow-up will be collected every 6 months for 3 additional years (2 years of response follow-up + 3 years of survival follow-up = total of 5 years of follow-up). BMS may request that survival data be collected on all treated/randomized participants outside of the protocol-defined window. At the time of this request, each participant will be contacted to determine their survival status unless the participant has withdrawn consent for all contacts or is lost to follow-up. Withdrawal of consent must be clearly documented. See [Section 5.1.3.3](#) for details.

c As of Protocol Amendment 06: Assessments necessary for monitoring safety (eg, safety labs, oxygen saturation, vital signs, physical exams, review of concomitant medications, AE/SAE reporting, etc) will continue per sub-protocol until the FU 3 visit. Tumor Scans, survival status follow-ups, and collection of subsequent treatment information will end once the participant has disease progression, or treatment discontinuation for any reason, whichever occurs first. Collection of samples for PK, ADA, biomarkers, as well as collection of data for patient-reported outcomes should be discontinued. The intent is to minimize the burden on study participants and site staff.

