**Table 4-1: Objectives and Endpoints**

Objectives	Endpoints

Primary
 
 
To assess the efficacy (ORR, DOR, and PFSR at 24 weeks) of each FRACTION-Gastric Cancer study treatment combination (relative to nivolumab in combination with ipilimumab, when applicable) in participants with advanced GC and/or EC
 
	
 
ORR, defined as the proportion of all treated participants with a BOR of CR or PR as assessed per RECIST v1.1 by investigator, median DOR, and PFSR at 24 weeks
 

Secondary
 
 
To investigate additional safety and tolerability of each FRACTION-Gastric Cancer study treatment combination in participants with advanced GC and/or EC
 
	
 
Incidence of AEs, SAEs, and AEs leading to discontinuation, deaths, and clinical laboratory test abnormalities
 

Tertiary/Exploratory
 
 
To assess the pharmacodynamic effects as a function of exposure, by evaluation of select biomarkers [REDACTED]
 
To explore potential associations between anti-tumor activity or safety and select biomarker measures [REDACTED]
 
To evaluate the PK of each IP component
 
To evaluate the immunogenicity of each IP, when applicable
 
To assess the OS in treated participants
 
To evaluate disease-related symptom improvement, as measured by the GaCS of the FACT-Ga and the ECS of the FACT-E in treated participants
 
To evaluate general health, functional status, and utility for health using the EQ-5D-3L in treated participants
 
	
 
Summary measures of change (or % change) from baseline or baseline level biomarker measurements [REDACTED]
 
Correlation (or similar appropriate measure of association) of biomarker measure [REDACTED]
 
Summary measures of PK parameters from serum concentration
 
Incidence of ADAs
 
OS rate at certain time points
 
Summary measures of EQ-5D-3L index and VAS scores, GaCS scores, and/or ECS scores, and corresponding change from baselines for each score
 

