### **5.1.3.2 Treatment**

The details of the Treatment Phase duration are provided in [Section 5.1](#). Further details of the study treatment administration are in each FRACTION-Gastric Cancer Sub-Protocol. Study assessments are to be collected as outlined in the On-treatment Procedural Outline(s) in each FRACTION-Gastric Cancer Sub-Protocol.

Assessment of response will be outlined for each combination therapy in the specific FRACTION-Gastric Cancer Sub-Protocol. Assessments of PR and CR must be confirmed at least 4 weeks later following initial assessment. Tumor progression or response endpoints will be assessed using RECIST v1.1 criteria for solid tumors (see [Appendix 5](#)).

Participants will generally be allowed to continue study treatment until the first occurrence of one of the following: 1) completion of 2 years of study treatment, 2) PD, 3) clinical deterioration suggesting that no further benefit from study treatment is likely, 4) intolerable toxicity, and 5) meeting of criteria for discontinuation of study treatment, as outlined in [Section 8.1](#). Individual participants with confirmed CR will be given the option to discontinue study treatment, on a case-by-case basis, after specific consultation and agreement between the investigator and the BMS Medical Monitor (or designee) in settings where the benefit/risk ratio justifies discontinuation of study treatment.

All participants will be treated as per [Section 5.1](#), unless criteria for study treatment discontinuation are met earlier (see [Section 8.1](#) in this FRACTION-Gastric Master Protocol and [Section 8.1](#) in the FRACTION-Gastric Cancer Sub-Protocol). Upon completion of the Treatment Phase, all participants will enter the Safety Follow-up Phase (see [Section 5.1.3.3](#) and [Table 2-3](#)).

As of Protocol Amendment 06, collection of blood or other biological samples for reasons other than safety monitoring (eg, PK, ADA, biomarkers, etc) should be discontinued. Please refer to [Table 2-3](#) and [Sections 9.5, 9.6, and 9.8](#).

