In the case of pregnancy, the investigator must immediately notify the BMS Medical Monitor (or designee) of this event. In most cases, the study treatment will be permanently discontinued in an appropriate manner (eg, dose tapering if necessary for participant safety). Please notify the BMS Medical Monitor (or designee) within 24 hours of awareness of the pregnancy. If the investigator determines a possible favorable benefit/risk ratio that warrants continuation of study treatment, a discussion between the investigator and the BMS Medical Monitor (or designee) must occur.

All participants who discontinue study treatment should comply with protocol-specified follow-up procedures as outlined in [Section 2](#). The only exception to this requirement is when a participant withdraws consent for all study procedures, including posttreatment study follow-up, or loses the ability to consent freely (ie, is imprisoned or involuntarily incarcerated for the treatment of either a psychiatric or a physical illness).

If study treatment is discontinued prior to the participant's completion of the study, the reason for the discontinuation must be documented in the participant's medical records and entered on the appropriate CRF page.

Additional study treatment-specific discontinuation criteria are provided in each FRACTION-Gastric Cancer Sub-Protocol.

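### Clinical-only progression is not a PFS event and, under Amendment 06, can no longer be documented by scan once treatment stops, so the 24-week PFS rate tends to read too high and needs one sensitivity estimate

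*Combined protocol and SAP*

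**What the plan says.** - **Endpoint.** The primary objective in Table 4-1 begins "To assess the efficacy (ORR, DOR, and PFSR at 24 weeks". Section 8.1.3 also calls PFSR a key endpoint.
- **Event.** Section 10.3.1 measures PFS from first dose "to the date of first objectively documented disease progression or death due to any cause". Progression judged only on clinical grounds is not in this definition.
- **Estimator.** For the 24-week rate: "Estimate by the Kaplan-Meier method and corresponding 95% CI will be derived based on Greenwood formula".
- **Censoring.** "Details on censoring scheme on time-to-event endpoints such as DOR, PFS, and OS will be described in the SAP". Section 10.3 says that the SAP is finalized before database lock; it is not part of the material available here.
- **Stopping treatment.** Section 5.1.3.2 lists, separately from progressive disease, "clinical deterioration suggesting that no further benefit from study treatment is likely". Section 8.1 has a similar item.
- **Scans after stopping.** Footnote c of Table 2-3 says that, as of Amendment 06, tumor scans, survival-status follow-up and subsequent-treatment collection "will end once the participant has disease progression, or treatment discontinuation for any reason, whichever occurs first". Section 5.1.3.3 repeats this, and Section 9.1 also lists treatment discontinuation as an end to tumor assessment. The note in the Table 2-3 row still describes scans at FU1 and FU3, which the footnote overrides from Amendment 06 on.
- **Deaths.** Appendix 3 makes death an SAE. Section 5.1.3.3 collects SAEs to 100 days after dosing stops.
- **Evaluability.** Section 10.2 makes a treated participant with measurable disease response-evaluable with "at least 1 postbaseline tumor measurement, 2) clinical progression, or 3) death".

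**The concern.** Read together, these provisions leave a gap. A participant who deteriorates clinically, stops treatment and has no objective progression by then has no later protocol scan on which progression could be documented. Survival-status follow-up has stopped too, so the remaining route to a PFS event is a death reported as an SAE within 100 days. If none is captured, the definition gives no event and the natural handling is censoring, probably at the last scan. Kaplan-Meier then treats a failing participant as having the same future risk as those who remain, and the 24-week rate moves up.

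The plan is not blind to clinical progression elsewhere. Without any post-baseline scan, it makes a participant response-evaluable (Section 10.2), and it is left out of the grounds for raising an arm's enrollment cap (Section 7.2).

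PFSR is among the measures that the sponsor reviews before stopping or continuing an arm (Sections 10.1, 10.1.1 and 10.1.2). For a Track 2 arm terminated at Stage 1, Table 10.3.1-1 marks only PFSR and OS.

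**Working it through.** **The plan's own figures.** The plan states no target, precision or power for PFSR. Its design figures concern response. Exact binomial calculation from the boundaries in Table 10.1-1 reproduces them: Track 1 has early stopping 0.673, false positive rate 0.048 and power 0.905 (stated 67%, 5%, 90%); Track 2 has 0.717, 0.046 and 0.902 (stated 72%, 5%, 90%). They neither support nor weaken this point, but they supply the arm sizes, 54 and 41.

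**Inputs from the documents.** Section 3.2.1 gives 12-month PFS rates of 17% (nivolumab plus ipilimumab) and 8% (nivolumab alone) from Study CA209032.

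**Assumed inputs.** Exponential PFS; a share c of 10% to 30% of progressions that are clinical only; scans every 6, 8 or 12 weeks; a median of 6 to 12 weeks from clinical progression to death. None of these is in the documents.

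**Step 1, a plausible 24-week rate S.** S = (12-month rate)^(24/52.18). This gives 0.17^0.460 = 44.3% and 0.08^0.460 = 31.3%, taken as the rates when clinical progression counts as an event.

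**Step 2, direction.** If a constant share c of the event hazard is censored instead, Kaplan-Meier converges to S^(1−c), which exceeds S for every c above 0.

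| S | c = 10% | c = 20% | c = 30% |
|---|---|---|---|
| 44.3% | 48.0% | 52.1% | 56.5% |
| 31.3% | 35.2% | 39.5% | 44.3% |

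The shift is about 4 to 13 points.

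**Step 3, scan schedule and deaths.** A simulation of 200,000 participants per setting censored clinical-only failures at the last scan. It was repeated with deaths within 100 days of stopping counted as events. Results for 8-weekly scans, with shifts against 31.3% and 44.3%:

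| S | c | Deaths not counted | Deaths counted, median 12 weeks | Deaths counted, median 6 weeks |
|---|---|---|---|---|
| 31.3% | 10% | 34.6% (+3.3) | 33.4% (+2.1) | 32.7% (+1.4) |
| 31.3% | 20% | 38.3% (+7.0) | 35.4% (+4.1) | 34.2% (+2.9) |
| 31.3% | 30% | 42.5% (+11.2) | 37.9% (+6.6) | 35.6% (+4.3) |
| 44.3% | 10% | 47.5% (+3.2) | 46.3% (+2.0) | 45.8% (+1.5) |
| 44.3% | 20% | 51.4% (+7.1) | 48.5% (+4.2) | 47.0% (+2.7) |
| 44.3% | 30% | 55.3% (+11.0) | 50.5% (+6.2) | 48.5% (+4.2) |

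Over all three scan intervals the range is +3.0 to +11.4 points without deaths and +1.2 to +6.7 with them.

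**Step 4, scale.** The standard error of one arm's rate, ignoring censoring, is √(S(1−S)/n). It runs from 6.3 points (S = 31.3%, n = 54) to 7.8 points (S = 44.3%, n = 41).

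**The case against.** The strongest reply is that no text says these participants are censored. The scheme is deferred to the SAP, where such cases are normally settled. That stands: the censoring is an inference from the event definition, and what the document shows is a missing rule. But the definition already excludes clinical progression, so a censoring scheme alone cannot turn it into an event.

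Second, scanning ends with treatment beyond doubt only from Amendment 06 (13 August 2021). The Table 2-3 note had given FU1 scans to all except those on subsequent therapy or with progression already treated beyond progression, and later scans to those with CR, PR, SD or NE at discontinuation. This also stands. The documents do not show how many participants were in their first 24 weeks after the amendment.

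Third, some provisions shrink the gap. Section 9.1 allows unscheduled assessments when progression is suspected, and Section 7.7.4 asks that symptoms needing palliative radiotherapy be checked for objective progression. Week 24 is Day 168, so for anyone last dosed on or after about Day 68 (168 − 100), deaths are collected through the landmark. These reduce the shift; they do not remove it for participants who stop without such a scan and survive the window.

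Fourth, the Simon guidelines rest on response counts, and PFSR has no threshold. That limits the consequence, but PFSR remains a primary endpoint and part of the review.

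Two stronger readings are tempting. A reader might infer that the plan counts clinical progression as failure for response. It does not: Sections 7.2 and 10.2 concern who is evaluable, a confirmed responder who later deteriorates stays a responder, and the final response rate uses all treated participants. A reader might also infer that arms with more clinical progression will look better. That is possible only if the share differs between arms, on which the documents are silent. With equal shares the formula barely moves a comparison: 44.3% against 31.3% is 13.0 points, and it becomes 12.8, 12.6 and 12.2 points at c = 10%, 20% and 30%.

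**Conclusion.** The point holds as a gap in a primary endpoint. Under the current text, a participant stopped for clinical progression without objective documentation becomes a PFS event only through a captured death and would otherwise, by inference, be informatively censored. The direction is upward. The size is illustrative: about 1 to 7 points when deaths within 100 days count and about 3 to 11 when they do not, on the assumptions listed. This is at most comparable to, or somewhat above, one arm's standard error of 6 to 8 points, but unlike sampling error it runs one way. It applies in full only to those who stop under Amendment 06 conditions and is smaller where earlier follow-up scans were done. Counting only objective progression or death is a legitimate primary definition and is not itself an error. The change is worth making, but the point does not invalidate the endpoint.

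**What to change.** Keep the primary PFS definition. Add to Section 10.3.1 and the SAP one sensitivity estimate of 24-week PFSR, per arm and track, in which treatment discontinuation for clinical progression or deterioration is an event on the discontinuation date. Show it beside the primary estimate and use both in the totality-of-data review. The SAP's censoring scheme should also state how these participants, and deaths after they stop, are handled in the primary estimate.

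The cost is SAP wording and one extra Kaplan-Meier row per arm. No new data item should be needed, because Section 8.1 already says that "the reason for the discontinuation must be documented" and entered on the CRF. One check is required: the CRF reason must separate clinical progression from overlapping reasons such as investigator discretion. The event also rests on open-label investigator judgement, so the estimate stays supportive.

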**Table 10.3.1-1: Analyses Planned for Each Track**

Track		ORR	DOR	PFSR	OS
Track 1	End of Simon Stages 1 and 2	X	X	X	X
Track 2	End of Simon Stages 1 and 2	X	X	X	X
	Early Termination at Simon Stage 1			X	X

**Track 1 - Anti-PD-1, Anti-PD-L1, and Anti-CTLA-4 Treatment-naïve Participants**

The following additional analyses will be performed for Track 1 anti-PD-1, anti-PD-L1, and anti-CTLA-4 treatment-naïve participants combined at end of Stage 2. These efficacy analyses will be performed when the study treatment arms have been fully enrolled and followed up for at least 6 months. A descriptive odds ratio and estimate of the difference in ORRs, along with corresponding 2-sided 95% CIs, will be provided to evaluate differences between the 2 randomized study treatment arms (FRACTION-Gastric Cancer study treatment combination arm and nivolumab in combination with ipilimumab control arm). Additionally, for each study treatment arm, the ORR and corresponding 95% CIs will be calculated using Clopper-Pearson method. A descriptive hazard ratio and corresponding 2-sided 95% CI of PFS and OS will be estimated in a Cox proportional hazards model using study treatment as a single covariate to evaluate difference between the 2 study treatment arms (experimental and control arms). The PFS and OS curves for each study treatment arm will be estimated. Two-sided 95% CIs for median PFS and OS will be computed. PFSR at 24 weeks and survival rates at certain time points (eg, 2 years) will be estimated. Associated 2-sided 95% CIs will be calculated.

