Each participant who is randomized will be assigned a unique randomization number. This is not the primary identifier for the participant, but is used for the randomization schedule. The primary identifier will be the PID described above, for use on the case report form (CRF) and source documents. A participant being re-randomized in Track 2 will be assigned a different randomization number but will retain the same PID. Randomization numbers will be assigned using a Central Randomization System in the order in which participants qualify for study treatment, not in the order of study enrollment. Randomization ratios within each track will be specified in each FRACTION-Gastric Cancer Sub-Protocol. If, within a given track, study treatment arms from more than 1 FRACTION-Gastric Cancer Sub-Protocol within the FRACTION-Gastric Cancer Master Protocol are simultaneously open to enrollment, then a new participant could be assigned to any of the open study treatment arms. In Track 1, participants will be randomized to newly added study treatment arms/study treatments (through FRACTION-Gastric Cancer Sub-Protocols) in a ratio specified in each new FRACTION-Gastric Cancer Sub-Protocol. New randomization schedules for new FRACTION-Gastric Cancer Sub-Protocols will be generated. If accrual for current FRACTION-Gastric Cancer Sub-Protocols is still ongoing, participants will be allocated to the existing randomization schedule or new randomization schedule based on a pre-specified allocation ratio. Details of allocation ratio will be specified in the new FRACTION-Gastric Cancer Sub-Protocol. In Track 2, participants will be randomized to existing study treatment arm/study treatments and newly added study treatment arm/study treatments with equal probability.

Pre-specified study treatment arm caps (according to Simon 2-stage [optimal] design) will be utilized to control the accrual for each study treatment combination arm under different tracks (Tracks 1 and 2). The cap for the nivolumab in combination with ipilimumab control arm under Track 1 will be set equal to the largest cap among its corresponding experimental arms. In the event that 1 or more participants go off study without being evaluable for response (ie, with no post-baseline tumor measurements and no evidence of clinical progression or death due to disease progression), the enrollment cap for that study treatment arm may be correspondingly raised if

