**Table 10.1-1: Simon 2-stage (Optimal) Design Considerations**

Track	Historical ORR/ Target ORR	Stage 1 Responders/Stage 1 n		Stage 2 Responders/Total n		Expected n with Historical ORR	Expected n with Target ORR
		Consider Futility	Go to Stage 2	Consider Futility	Consider Efficacy		
1	20%/40%	≤ 4/19	≥ 5/19	≤ 15/54	≥ 16/54	30.4	51.6
2	5%/20%	≤ 1/21	≥ 2/21	≤ 4/41	≥ 5/41	26.6	39.8

Note: Numbers of responses serve as a guideline; however, the totality of efficacy data will be considered when making decisions to terminate or continue an arm.

The Track 1 Simon 2-stage (optimal) design assumes a historical response rate of 20% and a target response rate of 40%, based on the observed response rate of approximately 24% for the nivolumab in combination with ipilimumab and approximately 12% for nivolumab monotherapy participants in Study CA209032. A false positive rate of 5% and power of 90% are used.

Because there is very little data available on participants with prior anti-PD-1, anti-PD-L1, or anti CTLA-4 treatment, the Track 2 design is not based on an observed historical response rate. Rather, the assumption is made that a response rate below 5% would not be worth further study and that a target response rate of 20% would be worth pursuing in this population. A false positive rate of 5% and power of 90% are used.

[figure not shown]
With regard to sample size, participants who are re-randomized to a different study treatment in Track 2 will be counted once for each randomization; participants who are retreated within the same study treatment arm will only be counted once.

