### 10.1.1 Track 1 - Anti-PD-1, Anti-PD-L1, and Anti-CTLA-4 Treatment-naïve Participants

As shown in Table 10.1-1, a minimum of 19 participants in each study treatment combination arm will be treated in Stage 1 for an initial evaluation of efficacy. If the total number of responses observed in Stage 1 is  $\leq 4/19$ , the study treatment combination arm would likely not be considered efficacious; otherwise, enrollment to Stage 2 will continue, and an additional 35 participants will be treated. If the total number of responses at the end of Stage 2 is  $\leq 15/54$ , the study treatment combination arm will be terminated for futility; if there are more than 15 responses observed at the end of Stage 2, the study treatment combination arm may be carried on for further treatment development. The totality of efficacy data and response profile for each combination arm will be considered when making decisions to terminate or continue an arm.

The operating characteristics of this Simon 2-stage (optimal) design are provided in Figure 10.1.1-1. With the stopping boundaries as shown in Table 10.1-1, if the study treatment combination arm has an ORR no better than the historical control at 20%, then there is a 95% overall chance of stopping for futility, with a 67% chance of stopping at Stage 1; there is a 5% false positive rate. If the study treatment combination arm has an ORR equal to the target of 40%, then there is a 90% chance of declaring efficacy after Stage 2, whereas if the true ORR is 25%, 30%, or 35%, the power would be 21%, 49%, or 75%, respectively.

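### If the Track 1 Stage 1 guideline is applied, the end-of-Stage-2 ORR comparison with nivolumab plus ipilimumab is modestly biased towards combinations that continue, and no adjusted estimate is planned.

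*Combined protocol and SAP*

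**What the plan says.** The Track 1 part of Section 10.3.1 sets out additional analyses for "treatment-naïve participants combined at end of Stage 2". On timing it says: "These efficacy analyses will be performed when the study treatment arms have been fully enrolled and followed up for at least 6 months". On content: "A descriptive odds ratio and estimate of the difference in ORRs, along with corresponding 2-sided 95% CIs, will be provided to evaluate differences" between a combination arm and the nivolumab plus ipilimumab arm. Descriptive Cox hazard ratios for PFS and OS are planned as well. No between-arm comparison is described for a combination stopped at Stage 1, and no estimate that allows for the two-stage selection is described.

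Section 10.1.1 gives the Stage 1 guideline. With 4 or fewer responses among 19, "the study treatment combination arm would likely not be considered efficacious; otherwise, enrollment to Stage 2 will continue", with 35 more participants for a total of 54. Table 10.1-1 gives the boundaries and expected sample sizes as "≤ 4/19 ≥ 5/19 ≤ 15/54 ≥ 16/54 30.4 51.6". Its note says that the counts are a guideline and that the totality of efficacy data decides.

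Section 7.2 sizes the control by its cap alone: "The cap for the nivolumab in combination with ipilimumab control arm under Track 1 will be set equal to the largest cap" among its experimental arms. No response threshold for the control is stated.

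**The concern.** The two arms of the comparison are not treated alike. A combination normally reaches the comparison because its own early responses were good enough, and those responses are then counted again in the final ORR. The control is filled to its cap whatever its responses. Randomization does not remove this, because the selection takes place after randomization and acts on the outcome.

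The primary objective in Table 4-1 is framed relative to nivolumab plus ipilimumab where applicable, and Section 3.1.1.1 says that the programme exists to choose combinations for registrational studies. A one-directional bias that is largest for combinations no better than control acts on exactly the arms that the programme wants to screen out.

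**Working it through.** **Inputs.** Stage 1 n = 19, continue on 5 or more, Stage 2 n = 35, total 54 (Table 10.1-1, Section 10.1.1). The Track 1 design "assumes a historical response rate of 20% and a target response rate of 40" percent; the control's reference ORR is about 24% (text under Table 10.1-1). Control n = 54, taken from the cap in Section 7.2. The allocation ratio is left to the Sub-Protocols, so 54 per arm is an assumption, as are equal true ORRs and no enrolment beyond 54.

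**Step 1: reproduce the plan's figures.** Let X1 ~ Bin(19, p) and X2 ~ Bin(35, p).
- P(stop at Stage 1) = P(X1 ≤ 4). At p = 20% this is 67.3% (plan: 67%).
- P(declare efficacy) = Σ over x ≥ 5 of P(X1 = x) · P(X2 ≥ 16 − x). This is 4.8% at 20% (plan: 5%) and 90.5% at 40% (plan: 90%). At 25%, 30% and 35% it is 21.6%, 49.8% and 75.5% (plan: 21%, 49%, 75%).
- Expected n = 19 + 35 · (1 − P(stop)). This is 30.4 and 51.6, as in the plan.

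**Step 2: expected ORR of a combination that continues under the strict rule.**

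E[ORR | continue] = (E[X1 | X1 ≥ 5] + 35p) / 54

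| True ORR | P(continue) | E[X1 given X1 ≥ 5] | Expected ORR at 54 | Bias |
|---|---|---|---|---|
| 20% | 32.7% | 5.80 | (5.80 + 7.0)/54 = 23.7% | +3.7 points |
| 24% | 49.4% | 6.09 | (6.09 + 8.4)/54 = 26.8% | +2.8 points |
| 30% | 71.8% | 6.63 | (6.63 + 10.5)/54 = 31.7% | +1.7 points |
| 40% | 93.0% | 7.90 | (7.90 + 14.0)/54 = 40.6% | +0.6 points |

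The control's expected ORR is p, so the last column is also the bias of the difference.

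**Step 3: effect on the planned summaries.** Both arms were enumerated in full, with a Wald 95% CI for the difference. The odds ratio is a geometric mean with 0.5 added to each cell; its true value is 1.

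| True ORR in both arms | Mean odds ratio | CI wholly above 0, with filter / without | Apparent advantage above 10 points, with filter / without |
|---|---|---|---|
| 20% | 1.26 | 5.7% / 2.7% | 18.5% / 9.2% |
| 24% | 1.17 | 4.6% / 2.7% | 17.2% / 10.7% |
| 40% | 1.02 | 3.2% / 3.0% | 14.9% / 14.0% |

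**Step 4: relax the rule.** Suppose that an arm with 4 or fewer responses continues with probability q. The documents give no value for q, so this is an assumption.

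| True ORR | q = 0 | q = 0.1 | q = 0.25 | q = 0.5 | q = 1 |
|---|---|---|---|---|---|
| 20% | +3.7 | +2.8 | +1.8 | +0.9 | 0 |
| 24% | +2.8 | +2.3 | +1.7 | +0.9 | 0 |

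**Step 5: scale against sampling error.** The 95% CI half-width is 1.96 · √(2p(1 − p)/54), which is 15.1 points at 20% and 16.1 at 24%.

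**Step 6: compare estimators.** Given continuation under the strict rule, the Stage 2 rate is unbiased. Averaging it over the possible Stage 1 counts, given the total s (Rao-Blackwellisation), keeps it unbiased and uses all 54 participants:

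p̃(s) = Σ C(19, x) · C(34, s − x − 1) / Σ C(19, x) · C(35, s − x), both sums over x = 5, …, 19

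An observed 16/54 = 29.6% becomes 27.7%. At a true ORR of 24%, the root mean squared error (RMSE) of the difference is 8.3 points for the planned comparison with its bias included, 8.7 for p̃ against 54 controls, and 10.2 for 35 Stage 2 participants against 35 concurrent controls.

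**The case against.** The strongest reply is that the plan imposes no hard filter. A reader might infer that every combination in the comparison has passed 5/19. The note to Table 10.1-1 calls the counts a guideline, and Section 10.1 keeps enrolment open during the Stage 1 evaluation, so an arm with 4 or fewer responses may reach the comparison. This stands: the values in Step 2 apply to strict use of the rule. The bias vanishes only if Stage 1 results never affect continuation, which would defeat the purpose of the design. Section 10.1 also lets relative performance inform the decision. If that includes a poor control result, it could add to the bias, by an amount that cannot be computed from the documents.

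A reader might also infer that a combination no better than control looks better on average. That is true only of arms that continue. At 20% and 24%, 67% and 51% of such arms fail the rule. Counting stopped arms at their Stage 1 ORR, the average combination ORR over all arms is about 2.2 and 2.6 points below the truth.

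Nor is this the only randomized evidence on the primary objective. PFS is compared between the same randomized arms, with PFSR at 24 weeks estimated for each, and Section 5.1.1 also randomizes Track 2 participants to nivolumab plus ipilimumab or a combination.

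The comparison is labelled descriptive and carries no decision rule, so no stated error rate is breached. This stands too, but bias belongs to the estimate, whether or not a test is attached.

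Finally, Section 10.3 refers to an SAP to be finalized before database lock, which is not part of the document, and the Sub-Protocols may add detail. Either might deal with the point. Section 10.3.1 itself defers only censoring details to the SAP. Amendment 06 closes the trial early, and the document does not show that any Track 1 arm reaches the end of Stage 2.

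**Conclusion.** The point holds in a conditional form. Among Track 1 combinations that continue, use of the Stage 1 guideline tilts the planned ORR difference and odds ratio towards the combination. At equal true ORRs the tilt is a few points where the combination is no better than the historical or control rate, and close to nil at the 40% target, where most arms pass anyway. It is one-directional but well inside the confidence interval, and it gets smaller the more freely failing arms are allowed to continue. The figures assume 54 per arm, equal true ORRs, no overrun, and a decision based on the first 19 participants. The document does not support reading this as a breach of a formal error rate or as grounds to drop the comparison. It is a low-cost improvement to how the estimate is reported.

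**What to change.** In the Track 1 part of Section 10.3.1, or in the SAP:

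1. Keep the planned descriptive odds ratio and difference on all participants, and state that they are conditional on the combination having continued past Stage 1.
2. Add as a sensitivity analysis the Rao-Blackwellised ORR for the combination arm, using all its participants, with the resulting difference from control.
3. As a simpler alternative to item 2, compare participants treated after those used in the Stage 1 decision with controls randomized over the same period. If more than 19 participants informed the decision, the cut-off should move to match.
4. Report whether the 5/19 guideline was followed for each arm, since the adjusted estimate is exactly unbiased only if it was.

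The cost is one extra table per Track 1 arm, with no added participants and no change to the design. Precision falls slightly with item 2 and more with item 3, by the RMSE figures above. That is why both belong beside the planned comparison and not in its place.
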